### 17.2.1. ALL TEAEs

Incidence (frequency and percentage) of TEAEs will be presented by System Organ Class (SOC) and Preferred Term (PT) by dose level for Stage 1 and by type of malignancy for Stage 2. Patients who experience more than one event within the same SOC and PT will be counted only once for that SOC and PT. Patients who experience more than one event within the same SOC but within different PTs will be counted once for that SOC and once for the different unique PT. All TEAEs will be further summarized by maximum severity and by relationship to study medication.

HMPL-523

---

### **17.2.2. RELATIONSHIP TO STUDY MEDICATION**

Relationship, as indicated by the Investigator, is classed as “not related” and “related”. TEAEs with a missing relationship to study medication will be regarded as related to study medication. If a patient reports the same AE more than once within that SOC/ PT, the AE with the worst relationship to study medication will be used in the corresponding relationship summaries.

### **17.2.3. SEVERITY**

Severity of AEs is graded from Grade 1 through 5 according to NCI CTCAE v5.0. The missing severity will be classified as grade 3. If a patient reports multiple TEAEs under the same SOC/PT, the TEAEs with the maximum severity (i.e., maximum grade) will be used in the summary.

### **17.2.4. TEAEs LEADING TO DOSE INTERRUPTION OF STUDY MEDICATION**

AEs leading to dose interruption will be identified as those records with a response of “Drug interrupted” to the item “Action taken with Study Treatment” in the eCRF page of “Adverse Events”. Frequency and percentage of TEAEs leading to dose interruption by SOC and PT will be presented by descending total frequency of SOC and descending total frequency of PT within SOC.

### **17.2.5. TEAEs LEADING TO DOSE REDUCTION OF STUDY MEDICATION**

AEs leading to dose reduction will be identified as those records with a response of “Dose reduced” to the item “Action taken with Study Treatment” in the eCRF page of “Adverse Events”. Frequency and percentage of TEAEs leading to dose reduction by SOC and PT will be presented by descending total frequency of SOC and descending total frequency of PT within SOC.

### **17.2.6. TEAEs LEADING TO DISCONTINUATION OF STUDY MEDICATION**

AEs leading to permanent discontinuation will be identified as those records with a response of “Drug permanently discontinued” to the item “Action taken with Study Treatment” in the eCRF page of “Adverse Events”. Frequency and percentage of TEAEs leading to treatment discontinuation by SOC and PT will be presented by descending total frequency of SOC and descending total frequency of PT within SOC.

HMPL-523

### 17.2.7. SERIOUS ADVERSE EVENTS

Treatment-emergent serious adverse events (TESAEs) are those TEAEs which are recorded as “Serious” on the Adverse Events page of the eCRF. A summary of serious TEAEs by SOC and PT will be presented by descending total frequency of SOC and descending total frequency of PT within SOC. TEAEs with a missing seriousness to study medication will be regarded as an SAE.

### 17.2.8. DRUG-RELATED SERIOUS ADVERSE EVENTS

Drug-related serious adverse events (SAEs) are these AEs which are recorded as “Related” and “Serious” on the Adverse Events page of the eCRF. A summary of serious drug-related TEAEs by SOC and PT will be presented by descending total frequency of SOC and descending total frequency of PT within SOC. TEAEs with a missing relationship to study medication will be regarded as related to study medication. TEAEs with a missing seriousness to study medication will be regarded as serious adverse events.

### 17.2.9. ADVERSE EVENTS OF SPECIAL INTEREST

AEs of special interest (AESI) will be identified based on the searching strategy listed in [Table 3](#). AESIs will be summarized based on MedDRA 27.1 by referring to the standardized queries in the table below.

**Table 3: AESI Categories**

TEAE of special interest	Search strategy
Hepatotoxicity	Drug related hepatic disorders - comprehensive search (SMQ Code 20000006 Narrow search). Sub-SMQ Liver related investigations, signs and symptoms (SMQ Code 20000008 Narrow search); Cholestasis and jaundice of hepatic origin (SMQ Code 20000009 Narrow search); Hepatitis, non-infectious (SMQ Code 20000010 Narrow search); Hepatic failure, fibrosis and cirrhosis and other liver damage-related conditions (SMQ Code 20000013 Narrow search);

HMPL-523

TEAE of special interest	Search strategy
	Liver-related coagulation and bleeding disturbances (SMQ Code 20000015 Narrow search).
Infective pneumonia	Infective pneumonia (SMQ Code 20000231 Narrow search).
Interstitial lung disease/Pneumonitis	Interstitial lung disease (SMQ Code 20000042 Narrow search).
Kidney injury	Acute renal failure (SMQ Code 20000003 Broad search).

SMQ = standard MedDRA query.

A summary of AESI's by SMQ and PT will be presented by descending total frequency of SOC and descending total frequency of PT within SMQ.

### 17.3. DEATHS

If any deaths are recorded on the "Death Details" page of the eCRF, the information will be presented in a summary table by stage 1 (dose level) and stage 2 (malignancy type) and a data listing.

### 17.4. LABORATORY EVALUATIONS

The following laboratory evaluations will be summarized in tables:

- Chemistry
- Coagulation
- Fasting lipid profile
- Hematology
- Leukocyte immunophenotyping
- Serum immunoglobulin
- Serum amylase and lipase
- Serum  $\beta$ -2 microglobulin
- Urinalysis

The following laboratory evaluations will be listed in listings:

- Chemistry
- Coagulation
- Fasting lipid profile

HMPL-523

- 
- Hematology
  - Leukocyte immunophenotyping
  - Serum immunoglobulin
  - Serum amylase and lipase
  - Serum  $\beta$ -2 microglobulin
  - Urinalysis
  - Pregnancy test
  - Viral serology

Quantitative laboratory measurements reported as “< X”, i.e. below the lower limit of quantification (LLQ), or “> X”, i.e. above the upper limit of quantification (ULQ), will be converted to X for the purpose of quantitative summaries, but will be presented as recorded, i.e. as “< X” or “> X” in the listings.

Descriptive statistics for all quantitative laboratory evaluations and change from the baseline will be presented in SI units for each visit.

For laboratory parameters graded by NCI CTCAE, version 5.0 (see [Appendix 2](#)), changes in CTC grade laboratory data will be summarized as shift table from baseline to worst post-baseline grade. Baseline CTCAE grade is derived from the last laboratory assessment prior to the first administration of study medication, as defined in [section 7.2](#). Worst (maximum) post-baseline CTCAE grade is derived with all measurements from the first dose administration of study medication to no more than 37 days after the last dose of study medication or new anti-cancer therapies, which comes earlier. Otherwise, the shift table will be presented by ‘normal’, ‘abnormal but not clinically significant’, ‘abnormal and clinically significant’.

All CTCAE Grade 1 or higher abnormalities in laboratory tests will be flagged in the listings.

The incidence of patients with the following abnormal liver function tests (Hy’s Law) at any time post baseline will also be summarized:

HMPL-523

- ALT or AST  $\geq 3$  x ULN and  $\leq 5$  x ULN
- ALT or AST  $\geq 5$  x ULN
- Total bilirubin  $\geq 2$  x ULN
- (ALT or AST  $\geq 3$  x ULN) and total bilirubin  $\geq 2$  x ULN
- (AST or ALT  $\geq 3$  x ULN) and total bilirubin  $\geq 2$  x ULN and ALP  $< 2$  x ULN

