5.1.2 Exclusion Criteria

Patients who meet any of the following criteria will be excluded from study entry:

1. Patients with primary central nervous system lymphoma.
2. Any of the following laboratory abnormalities:
 - a. Absolute neutrophil count $<1.0 \times 10^9/L$
 - b. Hemoglobin $<80 \text{ g/L}$
 - c. Platelets $< 50 \times 10^9/L$

NOTE: In the dose expansion stage, patients with cell counts below the thresholds listed above may be considered eligible if, in the investigator's opinion, the reason is believed to be splenic involvement or bone marrow infiltration. The investigator will discuss the eligibility of such patients with the sponsor, and only upon approval (confirmed in writing) by the sponsor will a patient with cell counts below the thresholds be enrolled in the study.

In the dose expansion stage, patients with Grade ≤ 2 neutropenia per CTCAE 5.0 and/or thrombocytopenia and with confirmed splenic involvement or bone marrow infiltration are eligible.

3. Inadequate organ function, defined by the following:
 - d. Total bilirubin $>1.5 \times \text{ULN}$ with the following exception:
 - Patients with known Gilbert's disease who have serum bilirubin level $\leq 3 \times \text{ULN}$ and normal AST and ALT may be enrolled.
 - e. AST and/or ALT $>2.5 \times \text{ULN}$ with the following exception:
 - In the dose expansion stage, patients with documented disease infiltration of the liver may have AST and ALT levels $\leq 5 \times \text{ULN}$.
 - f. Estimated creatinine clearance (CrCl) per Cockcroft-Gault:
 - Dose escalation stage of trial (Stage 1) – CrCl $< 40 \text{ mL/min}$
 - Dose expansion stage of trial (Stage 2) – CrCl $< 30 \text{ mL/min}$

- g. Serum amylase or lipase > ULN
- h. International normalized ratio (INR) > 1.5 × ULN or activated partial thromboplastin time (aPTT) > 1.5 × ULN

NOTE: Patients may be considered for the study if kidney function is impaired, but this impairment is believed to be a result of the patient's underlying disease. The investigator will discuss the eligibility of such patients with the sponsor, and only upon approval (confirmed in writing) by the sponsor will a patient with impaired kidney function due to underlying disease be enrolled in the study.

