6.4.5 Abnormal Liver Function Test Results

The finding of an elevated ALT or AST in combination with either an elevated total bilirubin ($> 2 \times \text{ULN}$) or clinical jaundice in the absence of cholestasis or other causes of hyperbilirubinemia is considered to be an indicator of severe liver injury (as defined by Hy’s Law). Therefore, investigators must report an AE of special interest upon the occurrence of either of the following:

- Treatment-emergent ALT or AST $\geq 3 \times \text{ULN}$ in combination with total bilirubin $> 2 \times \text{ULN}$
- Treatment-emergent ALT or AST $\geq 3 \times \text{ULN}$ in combination with clinical jaundice

The most appropriate diagnosis or (if a diagnosis cannot be established) the abnormal laboratory values should be recorded on the AE CRF (see Section 6.4.1) and reported to the sponsor’s designee as a nonserious AE of special interest (see Section 6.5.1).

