## HMPL-523

PARAM (SI Unit)	Hypo	Hyper	ATOXGR			
			GRADE 1	GRADE 2	GRADE 3	GRADE 4
Lactate Dehydrogenase (IU/L)		Blood lactate dehydrogenase increased	>ULN	~	~	~
Gamma Glutamyl Transferase (IU/L)		GGT increased	>ULN - 2.5 x ULN if baseline was normal; [a] 2.0 - 2.5 x baseline if baseline was abnormal [b]	>2.5 - 5.0 x ULN if baseline was normal; [a] >2.5 - 5.0 x baseline if baseline was abnormal [b]	>5.0 - 20.0 x ULN if baseline was normal; [a] >5.0 - 20.0 x baseline if baseline was abnormal [b]	>20.0 x ULN if baseline was normal; [a] >20.0 x baseline if baseline was abnormal [b]
Urate (umol/L)		Hyperuricemia	>ULN	~	~	~
pH	Acidosis	Alkalosis	pH >normal, but <=7.5	~	pH >7.5	~
			pH <normal, but >=7.3	~	pH <7.3	~
Leukocytes (10  /L)	White blood cell decreased	Leukocytosis	~	~	>100,000/mm 	~
			<LLN - 3000/mm  ; <LLN - 3.0 x 10e9 /L	<3000 - 2000/mm  ; <3.0 - 2.0 x 10e9 /L	<2000 - 1000/mm  ; <2.0 - 1.0 x 10e9 /L	<1000/mm  ; <1.0 x 10e9 /L

LLN = Lower limit of normal, ULN = Upper limit of normal; ~ = Not applicable

[a] If the baseline value is normal, the toxicity grade will be determined by the post-baseline value and the ULN (e.g., > ULN - 2.5 x ULN).

[b] If the baseline value is abnormal, the toxicity grade will be determined by the baseline value and the post-baseline value (e.g., 2.0 - 2.5 x baseline). This rule only applies to the abnormal baseline value that is higher than the normal range upper limit.

HMPL-523

---

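### SAP 17.4 counts liver-test thresholds under a Hy's Law label with no baseline condition and no timing rule, so elevations allowed at entry are counted and values from different dates could be paired

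*SAP*

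**What the plan says.** SAP 17.4 (Laboratory Evaluations) states that the incidence of patients with abnormal liver function tests, labelled Hy's Law, "at any time post baseline will also be summarized". The five rows are:

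1. ALT or AST from 3 to 5 × ULN, both ends included
2. ALT or AST at or above 5 × ULN
3. Total bilirubin at or above 2 × ULN
4. ALT or AST at or above 3 × ULN, and bilirubin at or above 2 × ULN
5. Row 4 with ALP below 2 × ULN

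The same section handles graded tests differently: "changes in CTC grade laboratory data will be summarized as shift table from baseline to worst post-baseline grade", using measurements up to "no more than 37 days after the last dose of study medication or new anti-cancer therapies". Under SAP Appendix 2, footnote b, when baseline is above normal "the toxicity grade will be determined by the baseline value and the post-baseline value".

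Two exceptions in Protocol 5.1.2, exclusion criterion 3, bear on these rows. In the expansion stage, "patients with documented disease infiltration of the liver may have AST and ALT levels" up to 5 × ULN; otherwise values above 2.5 × ULN exclude. Patients with known Gilbert's "disease who have serum bilirubin level" up to 3 × ULN may enter in either stage if AST and ALT are normal; otherwise bilirubin above 1.5 × ULN excludes.

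Protocol 6.4.5 defines the event that investigators must report as "Treatment-emergent ALT or AST" at or above 3 × ULN, combined with bilirubin above 2 × ULN or with clinical jaundice.

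**The concern.** The entry exceptions overlap the table's cut-offs, and the table does not look at baseline. A patient who enters with ALT at 4 × ULN from liver infiltration, or bilirubin at 2.5 × ULN from Gilbert's disease, and never changes is counted as having a post-baseline abnormality.

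The combined rows have a second gap. Nothing says that ALT/AST, bilirubin and ALP must come from the same sample, or from samples close in time. A programmer could take the worst value of each test over the whole follow-up and join them. An ALT rise in one month and an unrelated bilirubin rise much later would then sit in a row labelled Hy's Law. In row 5, one low ALP on any date would satisfy the ALP condition, which weakens it as a filter for cholestasis.

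Hepatotoxicity is an important identified risk (Protocol 2.3.2.1) and an AE of special interest (Protocol 6.2.3). The shift table takes one test at a time, so rows 4 and 5 are the only planned tabulation of the ALT/AST and bilirubin pair.

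**Working it through.** The plan gives no figure for this point, so there is nothing to reproduce. The check asks which rows an eligible patient can already meet at entry, and what one such patient does to a percentage.

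**Step 1: which rows exclusion criterion 3 leaves open at entry.** Limits without an exception are ALT/AST 2.5 × ULN and bilirubin 1.5 × ULN.

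| Row (SAP 17.4) | Stage 1 | Stage 2 |
|---|---|---|
| 1. ALT/AST 3 to 5 × ULN | No | Yes, infiltration, 3 to 5 × ULN |
| 2. ALT/AST ≥ 5 × ULN | No | Only at exactly 5.0 × ULN |
| 3. Bilirubin ≥ 2 × ULN | Yes, Gilbert's, 2 to 3 × ULN | Yes, Gilbert's, 2 to 3 × ULN |
| 4. Pair | No | No |
| 5. Pair with ALP < 2 × ULN | No | No |

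Rows 4 and 5 are closed for this reason. Bilirubin of 2 × ULN or more at entry needs the Gilbert's exception, which requires normal AST and ALT. ALT/AST of 3 × ULN or more needs the infiltration exception, which leaves the bilirubin limit at 1.5 × ULN. A patient with both conditions still cannot use both exceptions together. A search over a grid of values (0.2 to 7 × ULN in steps of 0.05, both stages, with and without each condition) gave the same table.

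**Step 2: the same stable patient in two outputs.** Take ALT at 4 × ULN throughout. Row 1 counts the patient, because 3 ≤ 4 ≤ 5. Under Appendix 2 the ratio to baseline is 4/4 = 1.0, below the 1.5 × baseline at which Grade 1 starts, so there is no grade. Take bilirubin at 2.5 × ULN throughout. Row 3 counts the patient. The ratio is 1.0, and Grade 1 needs more than 1.0 × baseline, so again there is no grade.

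**Step 3: timing in the combined rows.** Take a Gilbert's patient with two post-baseline samples: ALT 0.8 and bilirubin 2.5 × ULN, then ALT 3.2 and bilirubin 1.8 × ULN.

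- Worst of each test over time: ALT 3.2 ≥ 3 and bilirubin 2.5 ≥ 2, so row 4 counts the patient.
- Same sample: the first fails on ALT (0.8 < 3) and the second on bilirubin (1.8 < 2), so row 4 does not count the patient.

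**Step 4: size per patient** (Protocol Table 2, Stage 2).

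- Overall: 1/48 = 2.1 points
- HL: 1/25 = 4.0 points
- PTCL: 1/9 = 11.1 points

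The number of patients admitted under the exceptions is not given. If 1 to 5 of the 48 were affected (an assumption), the overall rate would move by 1/48 = 2.1 to 5/48 = 10.4 points.

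**Step 5: the bands.** A value of exactly 5 × ULN meets both row 1 (≤ 5) and row 2 (≥ 5).

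**The case against.** The strongest defence is that absolute thresholds make a sensitive and conservative screen. Protocol Appendix 13 states the biochemical Hy's Law criteria as multiples of ULN with no reference to baseline, and asks for expedited reporting before other causes have been evaluated. Baseline is shown elsewhere: SAP 17.4 also plans change from baseline by visit, the shift table and full listings. With 48 expansion patients, a spurious count could be traced. The combined rows use the word and, which can be read as same-sample; the SAP does not prescribe worst-of-each. The number affected may be zero, and no decision rule depends on these rows.

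Much of this stands, and it limits the point. A reader might infer four stronger things that the documents do not support:

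- **Stable baseline disease alone creates Hy's Law cases.** It cannot, as Step 1 shows; a new rise in the other test is also needed.
- **Entry abnormalities are reported as hepatotoxicity, or this table is its main read-out.** The AE of special interest comes from a separate MedDRA query search of TEAEs (SAP 17.2.9), and no document gives this table that status.
- **SAP 17.4 contradicts Protocol 6.4.5 and Appendix 2.** The first is an investigator reporting rule and the second a grading table. The rows are out of line with both, but neither governs them.
- **One such case changes the safety conclusion.** These are descriptive Phase I tables.

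The defence does not settle the rest. The SAP does not describe the rows as a broad screen; it labels them Hy's Law. The shift table cannot show the pair. An unstated timing rule leaves the result to the programmer.

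**Conclusion.** The point holds in a limited form. Rows 1 (Stage 2) and 3 (both stages) can count unchanged entry values as post-baseline abnormalities; row 2 can do so only at exactly 5 × ULN. Rows 4 and 5 cannot be met at entry, but a baseline elevation can supply one half, and with no timing rule the other half could come from another date. The bands overlap at 5 × ULN.

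The size per affected patient is 2.1 points overall in Stage 2, 4.0 in HL and 11.1 in PTCL; how many patients are affected is unknown.

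This rests on three assumptions. All 48 enrolled expansion patients were dosed and so are in the FAS. Entry followed exclusion criterion 3 without deviation. Liver tests did not rise between screening and the baseline value. The hepatotoxicity AESI summary and the CTCAE shift table are separate outputs and are not affected.

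**What to change.** Amend SAP 17.4 before database lock, which SAP section 2 allows:

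1. Count each threshold as treatment-emergent: met after baseline, with the baseline value below it. Show patients already above it at baseline on a separate line, using multiples of baseline as in Appendix 2, so that no case is hidden. In rows 4 and 5, apply the condition to the pair as a whole, so that a Gilbert's patient with a new, concurrent ALT rise still counts.
2. Require ALT/AST, bilirubin and ALP in the combined rows from the same sample, or within a short interval that the SAP states.
3. Make the bands non-overlapping at 5 × ULN.

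While the text is open, the SAP could also state the end of the counting window for these rows and reconcile its bilirubin cut-off (≥ 2 × ULN) with that of Protocol 6.4.5 (> 2 × ULN).

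The cost is SAP wording and minor reprogramming. The laboratory tests concerned are already in the schedule, so no new data are needed. The one downside is that counts for patients abnormal at entry move to a separate line.

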## 17.5. ECG EVALUATIONS

Results from the central ECG (Electrocardiogram) Reading Centre will be included in the reporting of this study.

The following ECG parameters will be reported for this study by dose levels in Stage 1 and by malignancy type in Stage 2:

- PR Interval (msec)
- RR Interval (msec)
- QRS Interval (msec)
- QT Interval (msec)
- QTcF Interval (msec) =  $QT \text{ interval} / \sqrt[3]{RR \text{ (ms)} / 1000}$
- HR (bpm)
- Overall assessment of ECG (Investigator's judgment):
  - Normal
  - Abnormal, Not Clinically Significant
  - Abnormal, Clinically Significant

The following summaries will be provided for ECG data:

- Actual and change from baseline by visit (for quantitative measurements).
- Overall assessment: shift from baseline to worst post-baseline.

All ECG data will be listed.

### 17.5.1. ECG MARKEDLY ABNORMAL CRITERIA

Markedly abnormal quantitative ECG measurements will be identified in accordance with the following predefined markedly abnormal criteria by visit:

HMPL-523

- 
- Absolute values for QTcF will be classified as:
    - > 450 to  $\leq$ 480 msec
    - > 480 to  $\leq$ 500 msec
    - > 500 msec
  - Change from Baseline for QTcF will be classified as:
    - >30 to  $\leq$ 60 msec increase from baseline
    - >60 msec increase from baseline
  - Absolute values for heart rate will be classified as:
    - <50 bpm
    - >100 bpm
  - Absolute values for PR interval will be classified as:
    - interval >200 msec
  - Absolute values for QRS interval will be classified as:
    - interval >120 msec

A summary table summarizing the number and percentage of patients with markedly abnormal ECG results will be presented. ECG data will also be presented in a listing.

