5.6.10 Electrocardiogram

All ECGs are required to be performed using a 12-lead tracing. Electrocardiogram measurements will include PR interval, QRS interval, RR interval, QT/QTcF interval, and heart rate.

Triplicate ECGs, approximately 2 minutes apart, should be performed at screening and pre-dose and at 4 hours \pm 15 minutes post dose on Days 1 and 15 of Cycle 1 in order to evaluate concentration-QT relationship for HMPL-523. Single ECGs will be conducted at any time on Day 1 of Cycle 2. From Cycle 3 onwards, ECGs will be performed as clinically indicated.

Electrocardiograms will be reviewed by the investigator to determine patient eligibility at screening. Additional ECGs and other cardiac monitoring will be provided as clinically indicated during the study.

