### **7.4. RETESTS, UNSCHEDULED VISITS AND EARLY TERMINATION DATA**

In general, for by-visit summaries, data recorded at the nominal visit will be presented. Unscheduled measurements will not be included in by-visit summaries but will contribute to the best/ worst case value where required (e.g. shift table).

In the case of a retest (visit-specific unscheduled visit number assigned), the latest non-missing measurement among all scheduled and unscheduled measurements for that visit will be used for by-visit summaries.

For ECG triplicate records, the mean value will be used for by visit summaries.

Early termination data of patients prematurely discontinued from study medication will be presented together with the end of treatment assessment for study medication completers.

Listings will include scheduled, unscheduled, retest and early discontinuation data.

HMPL-523

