## 7.6. WINDOWING CONVENTIONS

It is expected that there will be a variation between patients in the actual number of study days from the start of administration of study drug within each cycle defined as Day 1, to the dates that the scheduled visits occurred. To handle this, for tables and figures where data are grouped by visit, assessments will be categorized using visit windows based on study days (relative to the Day 1 of each cycle). The visit-window mapping is described in **Error! Reference source not found.** Visit-based summaries will be based on the windowed visits. All data, whether or not within the visit windows, will be presented in patient's listings. For windowed visits during the treatment cycles, if more than one visit occurs during a visit window, the visit closest to the scheduled day will be assigned to the windowed visit. If two visits are equidistant from the scheduled day, the later visit will be assigned to the windowed visit. If there are multiple assessments on the same day, the worst case will be used.

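### The ECG outlier table in SAP 17.5.1 has no worst on-treatment category, so a QTcF, heart rate, PR or QRS outlier found on an unscheduled ECG can be missing from it

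*SAP*

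**What the plan says.** SAP 17.5.1 lists bands for absolute QTcF (above 450, 480 and 500 msec), QTcF change (above 30 and 60 msec), heart rate (below 50, above 100 bpm), PR (above 200 msec) and QRS (above 120 msec). It introduces them with: "Markedly abnormal quantitative ECG measurements will be identified in accordance with the following predefined markedly abnormal criteria by visit". It then promises the table: "A summary table summarizing the number and percentage of patients with markedly abnormal ECG results will be presented". No any-time or worst-value category is named. The only worst-case ECG output, in SAP 17.5, is the shift in the investigator's overall normal/abnormal assessment.

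Three rules decide which ECGs reach a by-visit table:

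- SAP 7.4: "Unscheduled measurements will not be included in by-visit summaries". They may count towards a worst-case value where one is required.
- SAP 7.4, for a retest tied to a visit: "the latest non-missing measurement among all scheduled and unscheduled measurements for that visit will be used for by-visit summaries".
- SAP 7.6: "Visit-based summaries will be based on the windowed visits". Within a window, the visit nearest the scheduled day is used. The worst value is taken only among assessments on the same day.

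On timing, protocol 5.6.10 says: "From Cycle 3 onwards, ECGs will be performed as clinically indicated". The Amendment 5 summary of changes shows that this came in with that amendment. Footnote 18 of the schedule of activities, in both protocol and SAP, still describes an ECG on Day 1 of each cycle from Cycle 2. The schedule also marks an ECG at completion or early termination.

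**The concern.** A QT safety table should answer one question: how many patients crossed each threshold at any time on treatment? A by-visit classification answers a different one, namely how many crossed it on the single ECG chosen to represent each visit. An ECG taken off schedule for a clinical reason is a likely place for prolongation to appear, and it is the kind that the visit rules can set aside.

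The SAP handles this differently for the laboratory. SAP 17.4 summarises liver test abnormalities occurring at any point after baseline, and derives the worst CTCAE grade from all measurements in the on-treatment period. SAP 7.3 defines a worst post-baseline value for CTCAE grades and for the normal/abnormal assessment, but gives no rule for numeric ECG values. Because SAP 17.5.1 requires no worst value, the provision in SAP 7.4 that lets unscheduled data contribute has nothing to act on here. The number of patients above a given threshold can then be understated, and cannot be overstated, relative to an any-time count.

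**Working it through.** The plan states no figure to reproduce. The check sets the selection rules side by side and applies them.

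**1. SAP 7.4 alone.** An unscheduled ECG is left out of the by-visit summary. The retest exception admits an unscheduled value for its visit, but takes the latest value, not the worst. If a visit ECG read 505 msec and its retest 460 msec (assumed values), 460 would be summarised.

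**2. SAP 7.6 alone, window coverage.** The ECG window for a cycle from Cycle 3 runs from Day -3 to the end of cycle (EOC) minus 3, and for the last cycle to EOC. EOC is the day before the next cycle's Day 1, and there is no Day 0. So:

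- upper limit of cycle c = (D1 of c+1) − 1 − 3 = (D1 of c+1) − 4
- lower limit of cycle c+1 = (D1 of c+1) − 3

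The windows are adjacent, with no gap and no overlap. For an assumed patient with 28-day cycles whose last cycle is Cycle 8, Cycles 3 to 8 hold 6 × 28 = 168 treatment days. None falls outside a window and none falls in two. A lone clinically indicated ECG on any of these days is therefore assigned to a visit.

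**3. SAP 7.6, choice within a window (assumed values).**

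- Later cycle: ECGs on Day 3 (QTcF 460) and Day 10 (QTcF 505). Distances from Day 1 are 3 − 1 = 2 and 10 − 1 = 9. Day 3 is kept and the value above 500 msec is not tabulated.
- Any cycle with a Day 1 ECG: its distance is 0, so it displaces an unscheduled ECG on any other day in the window.
- Cycle 1, Day 15 window (Day 3 to EOC − 3): an unscheduled Day 10 ECG has distance 15 − 10 = 5 and loses to the scheduled Day 15 ECG at distance 0.

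**4. The two rules together.** For a lone unscheduled ECG from Cycle 3, 7.4 excludes it and 7.6 includes it. Where a scheduled ECG shares the window, 7.4 excludes the unscheduled one and 7.6 drops it unless it is nearer the scheduled day or taken on the same day.

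**5. Who is affected.** Protocol 7.1 gives 3 patients continuing treatment out of 48 in the expansion stage: 3/48 = 6.3%. Only these can be on the Amendment 5 schedule. The displacement in step 3 can affect any patient with a scheduled and an unscheduled ECG in one window.

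**6. Scale of one missed patient.** SAP 17.5 reports Stage 2 ECGs by malignancy. With enrolment from protocol Table 2, and assuming all enrolled patients were dosed: 1/48 = 2.1% overall, 1/25 = 4.0% in HL, 1/7 = 14.3% in CLL post-BTK.

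**The case against.** The strongest defence is SAP 7.6. A reader who stops at 7.4 might infer that prolongation found from Cycle 3 never enters the outlier table. The documents do not support that: the windows cover every on-treatment day from Cycle 3, so a lone unscheduled ECG can be tabulated.

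A reader might also infer that all ECGs from Cycle 3 contribute nothing. That fails too. ECGs only on clinical indication came in with Amendment 5, after enrolment closed and with about 3 patients on treatment. Footnote 18 describes ECGs each cycle, and the completion or early termination ECG is scheduled.

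A third inference is that pooling the pre-dose and 4-hour sets on Cycle 1 Days 1 and 15 would halve a change, for example from 10 to 5 msec. Nothing in the SAP averages the two sets. SAP 7.4 averages triplicates, which protocol 5.6.10 places about 2 minutes apart, and SAP 7.6 takes the worst case among same-day assessments. Whether the ECG baseline in SAP 7.2 is the mean of the pre-dose triplicate is worth a clarifying phrase, no more.

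Finally, the sentence promising the table gives no time basis, so a programmer could build it on an any-time count. All ECG data are listed, and unscheduled ECGs can feed the overall-assessment shift. All of this stands and narrows the point. It does not remove it: a listing is not an incidence, the shift does not report QTcF thresholds, and an any-time count should not depend on a generous reading.

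**Conclusion.** The point holds as a gap and a rule conflict. SAP 17.5.1 requires no worst on-treatment category for numeric ECG outliers, and neither rule that feeds by-visit tables selects the worst value across days. An outlier on an unscheduled ECG can be missing from the table in any cycle. For about 3 of 48 expansion patients, whether a clinically indicated ECG from Cycle 3 is counted depends on whether 7.4 or 7.6 is followed.

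The direction is towards undercounting. The size is unknown, because the documents give no count of unscheduled ECGs or of outliers. The 2.1%, 4.0% and 14.3% figures show only what one missed patient would mean. The window result assumes 28-day cycles with Cycle 8 last, although the adjacency argument does not depend on cycle length. In a descriptive single-arm Phase I safety table this calls for a change to the SAP wording; it does not undermine the study.

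**What to change.** - In SAP 17.5.1, count each patient once per category on the worst value in the on-treatment period of SAP 7.3, over all scheduled and unscheduled ECGs, with each replicate set averaged. For QTcF, QTcF change, PR and QRS the worst value is the maximum. Heart rate needs both the minimum and the maximum.
- Keep the by-visit rows as support.
- State whether 7.4 or 7.6 governs unscheduled ECGs in by-visit tables, and how the latest-value retest rule fits with the same-day worst-case rule.
- Reconcile footnote 18 in both schedules with protocol 5.6.10.
- Optionally, say in SAP 7.2 whether the ECG baseline is the mean of the pre-dose triplicate.

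The cost is a few sentences and one extra table block before database lock. The ECG data are already collected and due to be listed.
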